Sample Size:	A total of 420 randomised patients (210 per group) is foreseen assuming a withdrawal rate of approximately 20%, to achieve a total number of completed patients of 170 per group. For the primary endpoint of frequency of exacerbation (FOE), and a Poisson regression allowing for over-dispersion for FOE, with a two-sided significance level of 0.05, a treatment effect of 35% and a follow-up time of 1 year, with an FOE of 1.09 in the placebo group, this sample size will provide a power of 90%.

If the treatment difference effect size is 30% between the colistimethate sodium and placebo groups, the power with 170 completed patients per group will be 80%.

Population:Inclusion Criteria:

Subjects are eligible if they:

1. are able and willing to give informed consent following a detailed explanation of participation in the protocol and signed consent obtained;
2. are aged 18 years or older of either gender;
3. are diagnosed with NCFB by computerised tomography (CT) or high resolution CT (HRCT) as recorded in the subject's notes and this is their predominant condition being treated;
4. had at least 2 NCFB pulmonary exacerbations requiring oral or inhaled antibiotics or 1 NCFB pulmonary exacerbation requiring intravenous antibiotics in the 12 months preceding the Screening Visit (Visit 1) and had no NCFB pulmonary exacerbation with or without treatment during the period between Visit 1 and Visit 2;
5. have a documented history of *P. aeruginosa* infection;
6. are clinically stable and have not required a change in pulmonary treatment for at least 30 days before the Screening Visit (Visit 1);
7. have pre-bronchodilator FEV₁ ≥25% of predicted;
8. had a positive sputum culture for *P. aeruginosa* from an adequate sample taken at the Screening Visit (Visit 1) or during the screening period.

Exclusion Criteria:

Subjects are not eligible if they have/are:

1. known bronchiectasis as a consequence of cystic fibrosis (CF);
 2. known history of hypogammaglobulinaemia requiring treatment with immunoglobulin, unless fully replaced and considered immunocompetent by the Investigator;
 3. myasthenia gravis or porphyria;
 4. severe cardiovascular disease such as severe uncontrolled hypertension, ischaemic heart disease or cardiac arrhythmia and any other conditions that would confound the evaluation of safety, in the opinion of the Investigator;

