A fully blinded reassessment of trial size and power was undertaken for Promis I based on blinded data as of 15th January 2020 in 342 randomised, ITT population subjects. This evaluation gave a blinded annualised exacerbation rate estimate of 1.024 per year and an over-dispersion estimate of 0.273. For the hypothesised [CCI] reduction in the exacerbation rate with colistimethate sodium, this translates to annual event rate estimates for placebo and colistimethate sodium of 1.2701 vs 0.8256. The current data in Promis I, therefore, suggested that $n=145$ subjects per arm (290 total, unadjusted for dropout) were required to deliver 90% power, as compared to $n=170$ subjects per arm (340 total, unadjusted for dropout) stated in the protocol. Furthermore, the smallest observed reduction in the exacerbation rate with colistimethate sodium that will yield [CCI] in Promis I was computed to be [CCI].

This recalculation of the sample size was further refined to allow for a reduced overall exposure in Promis I arising due to some subjects dropping out of the study before completing 1 year of follow-up. This leads to a requirement for $n=188$ subjects per arm (376 total, adjusted for dropout) to detect a [CCI] reduction in the event rate with 90% power as compared to $n=210$ subjects per arm (420 total, adjusted for dropout) stated in the protocol; and with $n=188$ subjects per arm, the smallest observed rate reduction to yield [CCI] was computed to be [CCI].

It was, therefore, clear from the blinded data accrued in Promis I subjects to January 2020 that the $n=210$ subjects per arm stated in the protocol was unnecessarily high. At worst, the actual number of subjects required in Promis I is $n=188$ per arm (376 total) and this is inclusive of adjustment for the actual dropout rate seen in the trial itself. Given that, at the time of this sample size reassessment, a total of $n=372$ subjects had been randomised into Promis I, it could very reasonably be argued that very few, if any, further subjects were actually required to be randomised into the study to provide the required power to test the hypothesis that inhaled colistimethate sodium significantly reduces the exacerbation rate relative to placebo. Recruitment was, therefore, concluded with 377 randomised subjects.

CONFIDENTIAL

Sponsor:	Zambon S.p.A.	Protocol Number:	Z7224L01
----------	---------------	------------------	----------

4 Statistical Methodology

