The imputation model will include the following variables: treatment, pooled site, i.e. country, as detailed in Section 4.9.1, and use of stable concomitant therapy with oral macrolides.

The imputation will be performed according to the following strategies:

- missing at random: imputation based on the Missing At Random (MAR) assumption in all treatment groups. This analysis is based on the same assumption behind the model used for the primary efficacy analysis, however, it will allow for the inclusion in the analysis of all mITT patients;
- copy reference: imputation based on the data distribution of the placebo group in both treatment groups. This analysis mimics the case where discontinued subjects are in effect non-responders.

One thousand imputations will be performed and the analysis of the total number of pulmonary exacerbations (observed + imputed events) will be based on the same negative binomial model

CONFIDENTIAL

Sponsor:	Zambon S.p.A.	Protocol Number:	Z7224L01
----------	---------------	------------------	----------

used for the primary efficacy analysis. Estimates from the models will then be combined using Rubin's rule ^[2].

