  'Col. Sodium / Placebo: Visit 6' 0 0 1 0 0 0 -1 0,
  'Col. Sodium / Placebo: Visit 7' 0 0 0 1 0 0 0 -1 / cl;
  BY byvar; (optional)
  WHERE wherever; (optional)
RUN;
```

Notes:

- Visit represents the clinic visit;
- Psite represents the pooled site, i.e. country, as detailed in [Section 4.9.1](#);
- Med represents use of stable concomitant therapy with oral macrolides (e.g. azithromycin or erythromycin or clarithromycin) (Yes/No);
- Sub represents the Subject Number;
- Change represents the change from baseline to each visit of the variable;
- Baseline represents the baseline value of the variable;
- Treatment order: 1= Colistimethate Sodium, 2= Placebo.

CONFIDENTIAL

Sponsor:	Zambon S.p.A.	Protocol Number:	Z7224L01
----------	---------------	------------------	----------

- **Tables that require Prentice, Williams and Peterson Total Time model and 95% CIs of hazard ratios between treatments:**

```
PROC PHREG data=dset;
  CLASS treatment psite med;
  MODEL (tstart , tstop)*status(1) = treatment psite med / ties=Breslow;
  STRATA episode;
  HAZARDRATIO 'Col. Sodium vs Placebo' treatment / cl=both;
  BY byvar; (optional)
  WHERE wherever; (optional)
RUN;
```

Notes:

- Psite represents the pooled site, i.e. country, as detailed in [Section 4.9.1](#);
- Med represents use of stable concomitant therapy with oral macrolides (e.g. azithromycin or erythromycin or clarithromycin) (Yes/No);
- Status represents the censoring indicator (1 = censored);
- Treatment order: 1= Colistimethate Sodium, 2= Placebo;
- Dataset for the analysis should be adequately created: Subjects with no events have a single observation, while subjects with one event have two rows etc... A pair of variables (tstart, tstop) is used to define the time interval of risk. The start time (tstart) is generally equal to 0 for the first event and equals to the last recurrence stop time for further events. During an episode of pulmonary exacerbation, the subjects can't have another episode. Therefore, they are by definition not at risk for a next event during a previous episode. The stop time (tstop) is a recurrent event time (status = 1) or a censored time (status = 0). The event order should be denoted by variable episode.

- **Multiple Imputation for pulmonary exacerbation rate**

An example of SAS code is provided below for the **CCI** analyses pulmonary exacerbation rate.

Missing at random and copy reference imputation

```
PROC GENMOD DATA=dataset1;

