  MODEL count = treatment_d psite_d1-psite_dx med_d / OFFSET=log_years
  DIST=NEGBIN;
  /* >1000 imputations since some will be discarded due to convergence issues with the
  model */
  BAYES NBI=1000 NMC=11000 THIN=10 OUTPOST=dataset2 SEED=34783129;
RUN;

DATA dataset3;
  SET dataset2;
  RENAME treatment_d =c_treatment_d
  psite_d1-psite_dx=c_psite_d1-c_psite_dx
  med_d=c_med_d;
RUN;
```

CONFIDENTIAL

Sponsor:	Zambon S.p.A.	Protocol Number:	Z7224L01
----------	---------------	------------------	----------

```

PROC SQL;
  CREATE TABLE dataset4 AS
  SELECT dataset1.*, dataset3.*
  FROM dataset1, dataset3
  ORDER BY Iteration;
QUIT;

DATA dataset5;
  SET dataset4;
  BY Iteration;
  ARRAY c[*] c_psite_d1-c_psite_dx c_med_d;
  ARRAY x[*] psite_d1-psite_dx med_d;
  k=1/Dispersion;
  imp_subj=(years<365/365.25);
  years_imp=MAX(years,365/365.25);
  log_years_imp=LOG(years_imp);
  linpred_1=.;
  IF imp_subj THEN DO;
    years_miss=years_imp-years;
    linpred_1=Intercept;
    DO i=1 TO DIM(c);
      linpred_1+c[i]*x[i];
    END;
    linpred_mar=linpred_1+c_treatment_d*treatment_d;
    linpred_cr=linpred_1+c_treatment_d;
    y1hat_mar=years*EXP(linpred_mar);
    y2hat_mar=years_miss*EXP(linpred_mar);
    y1hat_cr=years*EXP(linpred_cr);
    y2hat_cr=years_miss*EXP(linpred_cr);
    CALL STREAMINIT(3231212);
    y2_mar=RAND('NEGBINOMIAL',(1+y1hat_mar)/(1+y1hat_mar+y2hat_mar),k+count);
    y2_cr=RAND('NEGBINOMIAL',(1+y1hat_cr)/(1+y1hat_cr+y2hat_cr),k+count);
    y_imp_mar=count+y2_mar;
    y_imp_cr=count+y2_cr;
  END;
  ELSE DO;
    y_imp_mar=count;
    y_imp_cr=count;
  END;
RUN;

```

Notes:

- dataset1 includes one record per patient;
- count represents the total number of exacerbations observed for each patient;
- treatment represents the treatment group (treatment order: 1 = colistimethate sodium, 2 = placebo);

CONFIDENTIAL

Sponsor:	Zambon S.p.A.	Protocol Number:	Z7224L01
----------	---------------	------------------	----------

- treatment_d represent the dummy variables for treatment group (values of the dummy variables: 0 for colistimethate sodium; 1 for placebo);
- Psite represents the pooled site, i.e. country, as detailed in [Section 4.9.1](#);
- psite d1-psite_dx represent the dummy variables for the (pooled) site;
- Med represents use of stable concomitant therapy with oral macrolides (e.g. azithromycin or erythromycin or clarithromycin) (Yes/No);
- med_d represents the dummy variable for use of stable concomitant therapy with oral macrolides;

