- years represents the follow-up time in years;
- log_years represents the logarithm of the follow-up time in years.

Analysis step

The imputed dataset obtained using the above SAS code will be finally analysed and the results will be combined.

```
ODS OUTPUT LSMeans=lsmeans1 Estimates=ratios1;
PROC GENMOD DATA=dataset5;
  BY Iteration;
  CLASS treatment psite med;
  /* MAR imputation */
  MODEL y_imp_mar = treatment psite med / OFFSET=log_years_imp DIST=NEGBIN;
  /* Alternative MODEL statement: copy reference imputation */
  MODEL y_imp_cr = treatment psite med / OFFSET=log_years_imp DIST=NEGBIN;
  LSMEANS treatment / ilink cl diff exp om;
  ESTIMATE 'Col. Sodium / Placebo' treatment 1 -1 / exp;
RUN;
```

```
DATA lsmeans2;
  SET lsmeans1 (WHERE=(zValue ne .));
  BY Iteration;
  IF first.Iteration THEN _Imputation_+1;
  IF _Imputation_ LE 1000;
RUN;
```

```
ODS OUTPUT ParameterEstimates=lsmeans3;
PROC MIANALYZE PARMS=lsmeans2;
  CLASS treatment;
  MODELEFFECTS treatment;
RUN;
```

```
DATA lsmeans4;
  SET lsmeans3;
  exp_est=EXP(Estimate);
  exp_lcl=EXP(LCLMean);
  exp_ucl=EXP(UCLMean);
RUN;
```

CONFIDENTIAL

Sponsor:	Zambon S.p.A.	Protocol Number:	Z7224L01
----------	---------------	------------------	----------

```
DATA ratios2 (RENAME=LBetaEstimate=Estimate);
  SET ratios1 (WHERE=(ChiSq ne .));
  BY Iteration;
  IF first.Iteration THEN _Imputation_+1;
  IF _Imputation_ LE 1000;
  Effect='Label';
RUN;
```

```
ODS OUTPUT ParameterEstimates=ratios3;
PROC MIANALYZE PARMS =ratios2;
  CLASS Label;
  MODELEFFECTS Label;
RUN;
```

```
DATA ratios4;
  SET ratios3;
  exp_est=EXP(Estimate);
  exp_lcl= EXP (LCLMean);
  exp_ucl= EXP (UCLMean);
RUN;
```

- **Tables that require Non-Parametric Randomization-Based Analysis of Covariance.**

The macro NParCov4, reported in [Appendix 4](#), will be applied with the following parameters.

For the analysis of pulmonary exacerbation score:

```
%NPARCOV4 ( outcomes = outcome,
             covars = psite med,
             trtgrps = treatment,
             strata = NONE,

             hypoth = NULL /*for p-value*/,
             hypoth = ALT /*for CI*/,

             transform = NONE,

             dsnin = dataset,
             dsnout = outdat,
             exact = %str(NO)
           );
```

For the analysis of annualised number of pulmonary CCI:

```
%NPARCOV4 ( outcomes = outcome,
             covars = psite med,
             trtgrps = treatment,
             strata = NONE,
```

CONFIDENTIAL

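### The SAP's printed multiple-imputation code for discontinuers uses 1 where the negative binomial shape k = 1/Dispersion belongs, so its MAR and copy-reference draws have the wrong mean unless the dispersion is 1

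*SAP*

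**What the plan says.** SAP 4.7.4.2 plans two multiple-imputation analyses of the primary endpoint for mITT subjects followed for less than 365 days: missing at random (MAR) and copy reference. Of the MAR version it says: "This analysis is based on the same assumption behind the model used for the primary efficacy analysis".

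SAP 4.14 prints the code. It fits a Bayesian negative binomial model and, for each posterior draw, sets "k=1/Dispersion". The expected counts in the observed and missing periods, y1hat and y2hat, are time multiplied by exp(linear predictor), with no dispersion factor. The MAR draw is then "y2_mar=RAND('NEGBINOMIAL',(1+y1hat_mar)/(1+y1hat_mar+y2hat_mar),k+count". The copy-reference draw has the same form, with "linpred_cr=linpred_1+c_treatment_d", which gives every subject the placebo coefficient.

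The block is introduced with "An example of SAS code is provided below", but the analysis step that follows says "The imputed dataset obtained using the above SAS code will be finally analysed".

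SAP Addendum 6.1.1 (signed July 2021) reports that the treatment effect was significant under MAR and not under copy reference. It gives this as the reason for a post-hoc tipping-point analysis, which imputes in a manner similar to MAR; no code is printed for it. The Note to File (signed April 2022) has Tables 14.2.1.1.4 and 14.2.1.1.4.1 rerun to correct a double-counting problem that it does not describe, and prints no revised formula.

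**The concern.** The draw mixes two parametrisations. A size of k + count comes from the gamma-Poisson model with shape k, and the matching probability has k where the code has 1. A 1 would be legitimate only if y1hat and y2hat had been multiplied by the dispersion, and they have not. The imputed counts therefore do not follow the fitted model, contrary to what 4.7.4.2 says of MAR.

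These are the pre-specified multiple-imputation checks of the primary result against dropout. With a dispersion below 1 the printed code imputes too many events. Under MAR the surplus arises in both arms at roughly their own rates, so the rate ratio moves little but its standard error grows. Under copy reference the surplus arrives at the placebo rate in both arms and dilutes the contrast more than the copy-reference assumption implies. The reported loss of significance under copy reference could then be partly a coding artefact.

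**Working it through.** **Inputs.** Dispersion: "an over-dispersion estimate of 0.273" (SAP 3.9, blinded reassessment). Annual rates 1.2701 (placebo) and 0.8256 (colistimethate), and 145 and 188 per arm without and with allowance for dropout (SAP 3.9). Withdrawal of about 20% (Protocol Summary, Sample Size). Code from SAP 4.14.

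**Scale of 0.273.** With variance mu + phi·mu², n per arm = (1.960 + 1.2816)² × (1/1.2701 + 1/0.8256 + 2 × 0.273) / ln(0.650)² = 144.1, which rounds up to the SAP's 145. Reading 0.273 as the shape instead gives 528. So k = 1/0.273 = 3.663.

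**Correct conditional distribution.** Let the frailty be Gamma(shape k, rate k). Given an observed count y1, it is Gamma(k + y1, rate k + y1hat). The missing count is then negative binomial with size k + y1, probability (k + y1hat)/(k + y1hat + y2hat) and mean (k + y1)·y2hat/(k + y1hat).

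**Printed distribution.** The size is the same and the probability is (1 + y1hat)/(1 + y1hat + y2hat), so the mean is (k + y1)·y2hat/(1 + y1hat).

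**Ratio, printed to correct:** (k + y1hat)/(1 + y1hat), whatever count was observed. For example, at the placebo rate with dropout at 0.5 years, y1hat = 0.635 and the ratio is (3.663 + 0.635)/(1 + 0.635) = 2.63.

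| Dropout time (years) | 0.05 | 0.25 | 0.5 | 0.75 | 0.95 |
|---|---|---|---|---|---|
| Placebo rate (placebo under MAR; both arms under copy reference) | 3.50 | 3.02 | 2.63 | 2.36 | 2.21 |
| Colistimethate rate (MAR) | 3.56 | 3.21 | 2.88 | 2.64 | 2.49 |

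**Monte Carlo check** (4 million subjects per scenario), mean missing count:

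| Rate, dropout time | True | Corrected code | Printed code | Ratio |
|---|---|---|---|---|
| 1.2701, 0.25 y | 0.952 | 0.953 | 2.875 | 3.02 |
| 1.2701, 0.5 y | 0.634 | 0.634 | 1.668 | 2.63 |
| 1.2701, 0.9 y | 0.126 | 0.126 | 0.283 | 2.24 |
| 0.8256, 0.5 y | 0.412 | 0.412 | 1.190 | 2.89 |

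**Sensitivity to the dispersion** (placebo rate, dropout at 0.5 years): ratio 6.5 at dispersion 0.1, 2.63 at 0.273, 1.61 at 0.5, 1.0 at 1, and 0.69 at 2, where the direction reverses.

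**Effect on the analyses.** Illustrative simulation: 188 per arm, the planned 35% reduction, dispersion held at 0.273, 20% dropout assumed uniform in time, treatment-only negative binomial model, 30 imputations, Rubin's rules, about 1,500 trials.

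| | Rate ratio, printed / corrected | SE of log rate ratio, printed / corrected | Significant trials, printed / corrected |
|---|---|---|---|
| MAR | 0.660 / 0.651 | 0.133 / 0.122 | 89% / 94% |
| Copy reference | 0.727 / 0.682 | 0.135 / 0.122 | 70% / 91% |

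Other copy-reference scenarios (600 trials each), significant trials, printed against corrected: 85% and 94% at 10% dropout; 65% and 91% at 23% dropout; 78% and 86% at dispersion 0.5 with 20% dropout; no difference at dispersion 1. The 23% is 1 − 145/188 read as a dropout proportion, which is an assumption. A separate large-sample calculation with 20% dropout gives copy-reference rate ratios of 0.73 (printed) and 0.68 (corrected).

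**The case against.** The code is labelled an example, the governing text in 4.7.4.2 states the method correctly, and the production programs went through quality control. So only the printed specification is shown to be wrong. That stands as a limit on the claim. It does not excuse the line, because the analysis step says that the dataset from this code is the one to be analysed.

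The link to copy reference is conjectural. The statement that significance was lost dates from July 2021, and the discontinuer and tipping-point tables were slated for rerun in April 2022. This also stands: the statement is not evidence that the slip changed a conclusion. Equally, the double-counting correction cannot be assumed to be this one.

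The factor of 2.2 to 3.6 rests on one blinded estimate from January 2020 in 342 subjects, and the posterior dispersion that the code would use is not given. It applies at the average planning rates, and a larger y1hat gives a smaller factor (1.67 at y1hat = 3). It concerns only the imputed part of dropouts' follow-up: with 20% dropout the total placebo rate rises from 1.27 to about 1.52 per year. The scale check is not unique either, since a quasi-Poisson factor of 1.273 also gives 145, though at means near 1 it implies much the same dispersion. These points qualify the size, not the algebra.

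Finally, with a dispersion below 1 the error works against the sponsor and cannot create an efficacy claim. That is true.

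**Conclusion.** The printed draw is wrong for both MAR and copy reference whenever the dispersion differs from 1. At the SAP's 0.273 the mean imputed count is about 2.2 to 3.6 times the correct value. The distortion is slight for the MAR rate ratio and material for copy reference, where it pulls towards no effect.

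The primary analysis is untouched, and the error would understate robustness rather than overstate it. The algebra rests only on the printed code. The trial-level percentages rest on the assumed dropout pattern, a fixed dispersion and a true 35% reduction; they describe hypothetical trials, not this one. Whether the reported tables carry the error cannot be seen from the documents. It should be fixed because it sits in a pre-specified check of the primary endpoint.

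**What to change.** - In both draws, replace the probability with (k + y1hat)/(k + y1hat + y2hat), or equivalently (1 + Dispersion·y1hat)/(1 + Dispersion·(y1hat + y2hat)).
- Confirm and document which formula the production programs used, including the tipping-point program, and whether the Note to File's double-counting correction was this one.
- If the printed line was used, regenerate Tables 14.2.1.1.4, 14.2.1.1.4.1, 14.2.1.1.4.2 and 14.2.1.1.4.3, and revisit the Addendum's statement on copy reference.
- A separate and minor point: Addendum 6.1.1 asks for the smallest shift at which p stays below 0.05. With MAR significant and the shift starting at 0, that is always 0; largest is meant.

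The cost is two lines of code, one check of the programs and one word in the Addendum. Tables need rerunning only if the check requires it.
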